#### 4.8.3.5 Percentage of subjects *responsive* (those showing objective symptoms leading to DBPCFC stop) to a cumulative dose $\geq 1,444$ mg peanut protein at the Month 12 DBPCFC

A subject is said to be *responsive* (showing objective symptoms leading to DBPCFC stop) to a cumulative dose of  $\geq 1,444$  mg of peanut protein at Month 12 if CRD  $\geq 1,444$  mg (as recalculated in [section 4.8.1.2](#)).

The number and percentage of subjects responsive to a cumulative dose  $\geq 1,444$  mg peanut protein at the Month 12 DBPCFC will be tabulated overall and for each screening ED subgroup on the ITT population, as well as on the FAS and PP population.

The percentage of subjects responsive to a cumulative dose  $\geq 1,444$  mg peanut protein at M12 will also be tabulated for each age group (4-5 and 6-11 years of age), on the overall ITT, FAS and PP populations.

The percentage of subjects responsive to a cumulative dose  $\geq 1,444$  mg peanut protein at M12 in the overall ITT population, using “Missing=failure” imputation, will be compared using the difference in treatment rates between the active treatment and placebo and the corresponding 2-sided Newcombe 95% CI [Number 8 in the pre-defined hierarchical order of the efficacy analyses]. The success criterion for this endpoint will be evaluated based on the lower bound of the 2-sided Wald 95% CI  $> 0\%$ . Additionally, a p-value based on the Wald test will be presented. In the case of sparse data (at least one of the

percentages is zero), no individual response rate confidence intervals and no p-value will be presented.

The same SAS® procedures as for the analysis of primary efficacy endpoint will be run. According to the sample size of each subgroup (if  $N < 50$ ), a Fisher's exact test will be performed instead of the Wald test, in which case exact 2-sided 95% CIs will be provided.

This analysis will be repeated on the FAS and PP population.

#### 4.8.3.6 Percentage of subjects *unresponsive* (those showing no objective symptoms leading to DBPCFC stop) to a cumulative dose $\geq 1,444$ mg peanut protein at the Month 12 DBPCFC

A subject is said to be *unresponsive* to a cumulative dose of  $\geq 1,444$  mg of peanut protein at Month 12 if:

- the sum of all doses given at Month 12, including repeated and partial doses is  $\geq 1,444$  mg; AND
- showing no objective symptoms which would trigger stopping of the DBPCFC (ED value entered by the investigator is missing).

The number and percentage of subjects *unresponsive* to a cumulative dose  $\geq 1,444$  mg peanut protein at the Month 12 DBPCFC will be reported and analyzed the same way as the percentage of subjects responsive to a cumulative dose  $\geq 1,444$  mg peanut protein at the Month 12 DBPCFC.

The analysis run on the ITT using "Missing=failure" imputation is the analysis [number 9 in the pre-defined hierarchical order of the efficacy analyses].

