#### 3.2.1.2 Secondary Efficacy Endpoint

The following secondary efficacy endpoints will be analyzed:

- The percentage of treatment responders at Month 12 in the active Viaskin® Peanut 250 µg group compared to the placebo group in each of the 2 screening ED strata;
- The percentage of treatment responders at Month 12 in the active Viaskin® Peanut 250 µg group compared to the placebo group in each of the 2 age subgroups (4 to 5 years-old; 6 to 11 years-old);
- The mean and median cumulative reactive dose of peanut protein and change from baseline at Month 12 in the active Viaskin® Peanut 250 µg group versus the placebo group, overall and for each screening ED stratum;

- The mean and median ED of peanut protein and change from baseline at Month 12 in the active Viaskin® Peanut 250 µg group versus the placebo group, overall as well as in each of the 2 screening ED strata;
- The percentage of subjects responsive (those showing objective symptoms leading to DBPCFC stop) to a cumulative dose  $\geq 1,444$  mg peanut protein at the post-treatment DBPCFC at Month 12 in the active Viaskin® Peanut 250 µg group versus the placebo group, overall as well as in each of the 2 screening ED strata;
- The percentage of subjects unresponsive (those showing no objective symptoms leading to DBPCFC stop) to a cumulative dose  $\geq 1,444$  mg peanut protein at the post-treatment DBPCFC at Month 12 in the active Viaskin® Peanut 250 µg group versus the placebo group, overall as well as in each of the 2 screening ED strata;
- The percentage of subjects unresponsive (those showing no objective symptoms leading to DBPCFC stop) to the highest dose of peanut protein, which is the percentage of subjects who pass the post-treatment DBPCFC at Month 12 in the active Viaskin® Peanut 250 µg group versus the placebo group, overall as well as in each of the 2 screening ED strata.

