#### *6.1.1.2 Time Interval and Doses*

The order of the formulas to be consumed during the first and the second day of the DBPCFC will be determined at random by the unblinded study-trained person preparing the formula using a specific randomization list provided to her/him for this purpose. Other members of the site staff (for example the Investigator, study coordinators, and study nurses), the subject/parents/guardians will remain blinded to the order of consumption until the end of the second day of the DBPCFC. Up to 7 days (1 week) between the 2 days of the DBPCFC will be permitted. The 2 days of the DBPCFC may be 2 consecutive days, but not the same day.

The challenge will consist on giving doses of peanut protein or placebo in gradually increasing doses at 30-minute intervals. This standard interval has been used safely in the past, but the Investigator may use clinical judgment to increase the intervals between doses if there is a concern that an objective reaction may be developing.

The starting dose is 1 mg of peanut protein for the entry/screening DBPCFC as well as the post-treatment DBPCFC; the maximum dose is 300 mg of peanut protein for the entry/screening DBPCFC and 2,000 mg for the post-treatment DBPCFC.

The peanut protein dose increments for the entry/screening DBPCFC are 1 mg, 3 mg, 10 mg, 30 mg, 100 mg, and 300 mg.

The entry/screening DBPCFC challenge is stopped at the 300 mg dose as a maximum, regardless of whether a reaction occurred before or not.

The peanut protein dose increments for the post-treatment DBPCFC are 1 mg, 3 mg, 10 mg, 30 mg, 100 mg, 300 mg, 1,000 mg and 2,000 mg.

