#### *6.1.1.4 Post-treatment DBPCFC to Peanut at Month 12*

The DBPCFC at Month 12 is conducted following exactly the same procedures as for the entry/screening DBPCFC. However, it is not stopped at the 300 mg dose. The challenge must instead be continued up to the last dose of 2,000 mg peanut protein or until objective reactions leading to stopping the DBPCFC occur.

Only **clear-cut OBJECTIVE immediate-type symptom(s) requiring treatment** will be considered as a permissible reason to stop the challenge and to determine the eliciting dose (highest dose given during the challenge) as well as the Cumulative Reactive Dose (CRD) of peanut protein. **Subjective symptoms will be graded but shall not count to stop the challenge.** The same instructions provided above to stop the challenge at the entry challenge will be followed to stop the challenge post-treatment.

During the duration of the study, DBPCFCs to other foods cannot be conducted for any randomized subject.

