#### 4.8.2 Primary Efficacy Analysis

The primary efficacy analysis is based on an endpoint that is derived from the Eliciting dose (ED).

The eliciting dose, i.e. dose at which objective symptoms leading to ending the DBPCFC occurred, is documented by the investigator in the eCRF.

In the following two cases, the ED at the M12 DBPCFC is not documented in the eCRF by the investigator:

- If the M12 DBPCFC is stopped without any objective symptoms leading to ending the DBPCFC (stopping rules) or
- if the subject took the 2,000mg dose without any objective symptom leading to ending the DBPCFC.

In those cases, the last dose given at M12 DBPCFC will be considered for ED value.

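### Hierarchy step 9 (unresponsive to ≥1,444 mg) fails children who tolerate 1,444 mg and first react at 2,000 mg, so it is almost the same test as step 14

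*SAP*

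**What the plan says.** The Month 12 challenge gives doses of "1 mg, 3 mg, 10 mg, 30 mg, 100 mg, 300 mg, 1,000 mg and 2,000 mg" (Protocol 6.1.1.2) and must be "continued up to the last dose of 2,000 mg peanut protein or until objective reactions leading to stopping the DBPCFC occur" (Protocol 6.1.1.4). Protocol 3.2.1.2 names as a secondary endpoint "The percentage of subjects unresponsive (those showing no objective symptoms leading to DBPCFC stop) to a cumulative dose" of 1,444 mg or more. It lists passing the whole challenge as a separate endpoint. It gives no further rule for deriving the first of these.

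SAP 4.8.3.6 supplies the rule for step 9, in two conditions. First, "the sum of all doses given at Month 12, including repeated and partial doses is" at least 1,444 mg. Second, the child is "showing no objective symptoms which would trigger stopping of the DBPCFC (ED value entered by the investigator is missing". SAP 4.8.3.7 (step 14) keeps the second condition and raises the total to 3,444 mg.

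SAP 4.8.2 settles when the ED is blank. It says: "The eliciting dose, i.e. dose at which objective symptoms leading to ending the DBPCFC occurred, is documented by the investigator in the eCRF". The field is left empty in only two cases: the challenge ended with no stopping symptoms, or "if the subject took the 2,000mg dose without any objective symptom leading to ending the DBPCFC". The same section has a partial-dose rule. If the child swallows no more of the last dose than the size of the previous one, the ED is recorded as the previous dose.

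Step 8 (SAP 4.8.3.5) counts children whose cumulative reactive dose (CRD) is at least 1,444 mg. Under SAP 4.8.1.2 the CRD is missing when the ED is missing. SAP 4.8.1.3 and Table 2 make each step conditional on success at the one before.

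**The concern.** A child with no stopping symptoms through the 1,000 mg dose has tolerated 1,444 mg. The blank-ED condition looks beyond that point, to the 2,000 mg dose, and turns the child into a failure if a reaction occurs there. The endpoint then no longer answers the question its threshold suggests, and two places in the hierarchy test nearly the same outcome. Step 9 also stands in front of steps 10-14, so a stricter rule at step 9 can close the path to the dose comparisons in the two screening ED subgroups (steps 10-13).

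**Working it through.** **1. The thresholds.** From the dose ladder, 1 + 3 + 10 + 30 + 100 + 300 + 1,000 = 1,444 mg, and 1,444 + 2,000 = 3,444 mg. Both SAP thresholds are reproduced: 1,444 mg is the total after the 1,000 mg dose, and 3,444 mg the total after the last dose.

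**2. Each possible outcome under the SAP rules.**

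| Month 12 outcome | Total given (mg) | ED entered | Step 8 | Step 9 | Step 14 | Tolerated 1,444 mg |
|---|---|---|---|---|---|---|
| Reacts at 1,000 mg | 1,444 | 1,000 | yes | no | no | no |
| Reacts at 2,000 mg | 3,444 | 2,000 | yes | **no** | no | **yes** |
| Takes 800 mg of the 2,000 mg dose, reacts | 2,244 | 1,000 | yes | **no** | no | **yes** |
| Passes all doses | 3,444 | blank | no | yes | yes | yes |
| Stops after 1,000 mg, no symptoms | 1,444 | blank | no | yes | no | yes |
| Takes 1,500 mg of the 2,000 mg dose, no symptoms | 2,944 | blank | no | yes | no | yes |

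The second and third rows are the mismatch. Steps 9 and 14 separate only in the last two rows, that is, symptom-free challenges with a total from 1,444 to below 3,444 mg. Protocol 6.1.1.4 does not plan for such an ending; where it is followed, those rows are empty and the two steps coincide.

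**3. Size, on assumed rates.** The documents give no rates for these outcomes. I used 220 v 110 (SAP 4.12) and enumerated all binomial outcomes. The success rule was a Newcombe lower bound above 0, where the bound is (p1 − p2) − √[(p1 − L1)² + (U2 − p2)²] and L1 and U2 are Wilson 95% limits. As a check on the method, it gives 89.2% for the overall primary criterion (SAP table 90%), 99.99% for Stratum 1 (SAP 99%) and 94.6% for Stratum 2 (SAP 95%).

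- Assume 15% v 5% never react, and 10% v 3% first react at 2,000 mg.
- SAP rule: 15% v 5%, power 81%.
- Tolerance of 1,444 mg: 15 + 10 = 25% v 5 + 3 = 8%, power 98%.
- Wider range: never-react rates from 5% v 1% to 15% v 3% give about 39% to 96% under the SAP rule. Adding first reactions at 2,000 mg of 5% v 2% to 15% v 5% gives about 66% to more than 99% for tolerance of 1,444 mg.

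**4. How far a gain would travel.** I kept the 15% v 5% and 10% v 3% rates, further assumed 10% v 2% reacting at 1,000 mg, and simulated the counts in each arm (multinomial, 400,000 draws). Steps 1-7 were not modelled.

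- Steps 8 and 9 both succeed (the gate to step 10): 79% under the SAP rule, 96% under the tolerance rule.
- Steps 8, 9 and 14 all succeed: about 79% under either rule.

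Step 14 needs the never-react comparison whatever step 9 says.

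**The case against.** The best defence is that the SAP reads the endpoint literally. If ≥1,444 mg means any cumulative dose at or above that figure, a child stopped by symptoms at 3,444 mg did respond to such a dose. Steps 8 and 9 then form a tidy pair: among children given at least 1,444 mg with a usable challenge, step 8 takes those who had a stopping reaction and step 9 those who did not. The protocol attaches the same parenthesis about stopping symptoms to both unresponsive endpoints, so some overlap was there from the start. That reading is open, and for this reason one cannot say that the SAP contradicts the protocol. It does not remove the redundancy, however: step 9 remains almost the same comparison as step 14, and tolerance of 1,444 mg is still tested nowhere.

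A reader might infer that the lost power carries through the rest of the hierarchy. The calculation does not support that for step 14. A reader might also infer that children reacting at 2,000 mg are lost to the efficacy analysis. They are not. A child with ED 2,000 mg is a responder on the primary endpoint, contributes a high value to steps 4 and 5, and counts as a success at step 8. Finally, it would go too far to call steps 9 and 14 identical without qualification, because the SAP provides for challenges that end early without symptoms. How many there will be is unknown.

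**Conclusion.** The point stands as a matter of definition and needs no assumed rates. Under SAP 4.8.3.6 a child who tolerates 1,444 mg and first reacts to the 2,000 mg dose fails step 9. Step 9 is distinct from step 14 only through symptom-free challenges ended between the two totals.

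The size of the power effect is illustrative: 81% against 98% in the worked example. It requires first reactions at 2,000 mg to be more frequent on active than on placebo, which is plausible but not documented. Any benefit from changing the rule is confined to step 9 and the gate to steps 10-13. The SAP rule is the stricter of the two. It does not inflate type I error, and it leaves the primary result untouched. The point should be settled before unblinding but does not threaten the trial's main conclusion.

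**What to change.** Before unblinding, define step 9 from the dose records: all doses through 1,000 mg taken, and no stopping symptoms at any dose up to and including the 1,000 mg dose. Count as successes the children whose first stopping reaction follows any full or partial intake of the 2,000 mg dose. This must include those whose ED is recorded as 1,000 mg under the partial-dose rule in SAP 4.8.2, so the ED field alone cannot drive the derivation. Protocol 6.1.1.3 has doses given and time of symptom onset recorded, and these can be used. Leave step 14 as it is.

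The cost is a change of SAP wording and one derived flag, with no new data. There is a small downside to state in the SAP: children who first react at the 2,000 mg dose will count under both step 8 and step 9, so those two steps will no longer be mutually exclusive. If the sponsor prefers the literal reading, the SAP should say so and explain why steps 9 and 14 both keep a place in the hierarchy.

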#### 4.8.3.7 Percentage of subjects *unresponsive* (those showing no objective symptoms leading to DBPCFC stop) to the highest dose of peanut protein which is the percentage of subjects who pass the Month 12 DBPCFC

Subjects *unresponsive* to the highest dose of peanut protein are defined as subjects:

- for which the sum of all doses given at Month 12, including repeated and partial doses is  $\geq 3,444$  mg; AND
- showing no objective symptoms which would trigger stopping of the DBPCFC (ED value entered by the investigator is missing).

The analysis of this variable will be performed the same way as for the two preceding variables. The analysis run on the ITT using "Missing=failure" imputation is the analysis number 14 in the pre-defined hierarchical order of the efficacy analyses.

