### 6.1 Efficacy Variables

#### 6.1.1 Response to Treatment – DBPCFC to Peanut

The DBPCFC to peanut will be performed at study entry and post-treatment at Month 12 in order to assess the primary efficacy endpoint (percentage of treatment responders in the active Viaskin® Peanut 250 µg group compared to the placebo group), the main secondary efficacy endpoint (percentage of treatment responders in the active Viaskin® Peanut 250 µg group compared to the placebo group in each screening ED stratum), as well as the other secondary efficacy endpoints (mean and median cumulative reactive/ED of peanut protein and change from baseline at Month 12; percentage of subjects responsive/unresponsive to a cumulative dose  $\geq 1,444$  mg peanut protein at Month 12; percentage of subjects unresponsive to the highest cumulative dose of peanut protein at Month 12).

The DBPCFC is the gold standard to diagnose and assess food allergy. The challenges will occur over 2 days; the subject will be gradually fed increasing amounts of standardized blinded oral formulas containing either peanut protein during one of the two days of the challenge, or without any peanut protein during the other day of the challenge, or vice et versa. Challenges must take place under direct medical supervision in a hospital/clinic setting with resuscitation equipment and emergency medications and staff immediately available. An IV line can be established prior to the challenge when judged necessary by the Investigator. In that case, a local anesthetic cream can be used for establishing the IV line. If a site prefers to have the subjects come to the hospital the day before the conduct of the DBPCFC, to get them ready for the following day, this is allowed and will not be considered an SAE.

Subjects should wash out any antihistamines for the minimum period of time specified in the table in [APPENDIX 4](#)) prior to performing the DBPCFC.

Subjects will not be allowed to use long-acting  $\beta 2$ -agonists within 36 hours prior to the DBPCFC. Subjects who received more than a 3-day course of systemic corticosteroids within 4 weeks of the DBPCFC should have the DBPCFC delayed to allow for 4 weeks of corticosteroid wash-out. If a subject has a reaction during the first day of the DBPCFC that requires treatment with systemic corticosteroids on the first day, the subject has to wait at least 3 days before performing the second day of the DBPCFC.

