**More specifically, the food challenge must be stopped if:**

- There is  $\geq 1$ -point rise in an objective symptom from 1 category in the OFC Symptom Score Sheet with the following exceptions:

The followings require a  $>1$ -point rise to stop the challenge if present alone

- Urticaria
- Rash
- Laryngeal (if explained and not persistent)

The followings require a  $>2$ -point rise to stop the challenge if present alone:

- Pruritus
- Sneezing/Itching
- Nasal Congestion
- Rhinorrhea
- Conjunctivitis

- There is  $\geq 1$ -point rise in an objective symptom from  $\geq 2$  categories in the OFC Symptom Score Sheet with the following exceptions:

The following exceptions require a  $\geq 2$  point rise in one of these symptoms plus a  $\geq 1$ -point from another category:

- Pruritus
- Sneezing/Itching
- Nasal Congestion
- Rhinorrhea
- Conjunctivitis

Conjunctivitis (erythema of the conjunctiva) is not mentioned in the OFC Symptom Score Sheet but is an objective symptom that could appear during the challenges and is pre-specified in the e-CRF. Please also report in the e-CRF with a grade when this occurs, together with any other symptoms that could occur during the challenge.

In case of symptoms that develop but do not meet stopping rules, consider allowing 30 additional minutes to see if the reactions subside or progress to meet stopping criteria. You can also repeat the dose or step up at your discretion.

Further details are provided in the study-specific Manual of Procedures for the DBPCFC that will be provided to the sites.

In case of subjective symptoms, for example mouth pruritus, throat pruritus, nausea, abdominal pains or any other subjective symptoms, the severity of which might signify that objective symptoms are developing according to the Investigator's judgment, the time between the previous dose and the next dose might be extended to see how the subject's symptoms evolve. The same dose of peanut protein can be repeated to check whether the subjective symptoms reappear or not and with what severity, or whether objective symptoms now appear. If objective symptoms meeting stopping rules appear, they should be treated and the food challenge will be stopped. The dose given that

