#### Secondary efficacy endpoints:

The following secondary efficacy endpoints will be analysed.

- Percentage of treatment responders at Month 12 in the active Viaskin® Peanut 250 µg group compared to the placebo group in each of the 2 screening ED subgroups.
- Percentage of treatment responders at Month 12 in the active Viaskin® Peanut 250 µg group compared to the placebo group in each of the 2 age subgroups: 4 to 5 years-old; 6 to 11 years-old.
- Mean and median cumulative reactive dose of peanut protein and change from Baseline at Month 12 in the active Viaskin® Peanut 250 µg group versus the placebo group in the overall population, and for each screening ED subgroup.
- Mean and median ED of peanut protein and change from Baseline at Month 12 in the active Viaskin® Peanut 250 µg group versus the placebo group in the overall population, and for each screening ED subgroup.
- Percentage of subjects responsive (those showing objective symptoms leading to DBPCFC stop) to a cumulative dose  $\geq 1,444$  mg peanut protein at the Month 12 DBPCFC in the active Viaskin® Peanut 250 µg group versus the placebo group in the overall population, and for each screening ED subgroup.
- Percentage of subjects unresponsive (those showing no objective symptoms leading to DBPCFC stop) to a cumulative dose  $\geq 1,444$  mg peanut protein at the

Month 12 DBPCFC in the active Viaskin® Peanut 250 µg group versus the placebo group in the overall population, and for each screening ED subgroup.

- Percentage of subjects unresponsive (those showing no objective symptoms leading to DBPCFC stop) to the highest dose of peanut protein, which is the percentage of subjects who pass the Month 12 DBPCFC in the active Viaskin® Peanut 250 µg group versus the placebo group in the overall population, and for each screening ED subgroup.

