##### Partially ingested dose:

If the last dose given is only partially ingested by the subject prior to the DBPCFC stop, then the ED reported by the investigator is:

- the previous dose given if the quantity of the last dose given actually ingested by the subject is  $\leq$  to the previous dose ingested;
- the last dose given if the quantity of the last dose given actually ingested by the subject is  $>$  than the previous dose ingested.

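### SAP 4.8.3.7 defines passing the Month 12 challenge by a 3,444 mg dose sum, not by taking the 2,000 mg dose, so pass status can contradict the SAP's own eliciting-dose rule in symptom-free children

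*SAP*

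**What the plan says.** The endpoint is named in SAP 3.2 as "Percentage of subjects unresponsive (those showing no objective symptoms leading to DBPCFC stop) to the highest dose of peanut protein". Protocol 3.2.1.2 likewise refers "to the highest dose of peanut protein, which is the percentage of subjects who pass the post-treatment DBPCFC at Month 12". SAP Table 2 places it at step 14, the last, with success if the lower 95% Newcombe bound for the difference exceeds 0%.

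SAP 4.8.3.7 then makes it operational with two conditions joined by AND. The child is one "for which the sum of all doses given at Month 12, including repeated and partial doses is" at least 3,444 mg, and there were no objective symptoms that would stop the challenge, which is read from a blank investigator ED. Neither condition mentions the 2,000 mg dose.

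Three other places bear on this:

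- **Ladder.** Protocol 6.1.1.2 gives the increments: those for the "post-treatment DBPCFC are 1 mg, 3 mg, 10 mg, 30 mg, 100 mg, 300 mg, 1,000 mg and 2,000 mg".
- **Repeats.** Protocol 6.1.1.3 tells investigators, for symptoms short of the stopping rules, "You can also repeat the dose or step up at your discretion". Protocol 6.1.1.4 applies the same procedures at Month 12.
- **Partial doses.** SAP 4.8.2 has a rule for the ED: "If the last dose given is only partially ingested by the subject prior to the DBPCFC stop", the ED is the previous dose when the amount eaten does not exceed that dose, and the last dose when it does. SAP 4.8.3.4 applies this rule to challenges that ended without stopping symptoms.

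The name is not uniform. Protocol 6.1.1 describes the endpoint as the "percentage of subjects unresponsive to the highest cumulative dose of peanut protein at Month 12", and SAP 4.13 also speaks of a highest cumulative dose.

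**The concern.** An endpoint named for the top dose is decided by a running total that can be reached without that dose, or missed although it was eaten. The blank ED does not repair this. Under SAP 4.8.2 the ED is blank both when a challenge ends early without stopping symptoms and when the 2,000 mg dose is taken without them, so the sum alone separates the two.

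One child can then carry an ED of 1,000 mg at step 5 and a pass at step 14, or an ED of 2,000 mg and no pass. Passing is the strictest efficacy statement in the hierarchy, so its definition should say what its name says.

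**Working it through.** **Plan's own figures.** From the ladder in Protocol 6.1.1.2:

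1 + 3 + 10 + 30 + 100 + 300 + 1,000 + 2,000 = 3,444 mg, the SAP cut-off exactly. Up to the 1,000 mg step the sum is 1,444 mg. The worked example in SAP 4.8.1.2, with 300 mg repeated, gives 1 + 3 + 10 + 30 + 100 + 2 × 300 = 744 mg, as stated there. The cut-off therefore has no slack.

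**General condition.** Take a child without stopping symptoms who ate all earlier steps. Let x be the amount eaten of the 2,000 mg portion and R the total of repeated doses.

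- Pass under 4.8.3.7: 1,444 + R + x ≥ 3,444, so x ≥ 2,000 − R.
- ED under 4.8.2: 2,000 mg if x > 1,000, otherwise 1,000 mg. In the ITT analysis 4.8.3.4 takes the larger of this and the screening ED, which is at most 300 mg and so changes nothing.

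The two disagree in two regions:

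- pass with an ED of 1,000 mg when 2,000 − R ≤ x ≤ 1,000, which needs R ≥ 1,000;
- no pass with an ED of 2,000 mg when 1,000 < x < 2,000 − R, which needs R < 1,000.

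**Cases.**

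| Child, no stopping symptoms | Sum (mg) | 4.8.3.7 | ED (mg) |
|---|---|---|---|
| Full ladder | 3,444 | pass | 2,000 |
| Full ladder plus any one repeat | 3,445 to 5,444 | pass | 2,000 |
| Any one repeat up to the 1,000 mg step, 2,000 mg not started | 1,445 to 2,444 | no pass | 1,000 |
| 1,000 mg repeated once, 1,000 mg of the 2,000 mg eaten | 1,444 + 1,000 + 1,000 = 3,444 | **pass** | **1,000** |
| 1,000 mg repeated twice, 2,000 mg not started | 1,444 + 2,000 = 3,444 | **pass** | **1,000** |
| No repeat, 5 mg of the 2,000 mg left | 3,439 | **no pass** | **2,000** |
| No repeat, 15 mg of the 300 mg step (5%) recorded as uneaten, all 2,000 mg eaten | 3,429 | **no pass** | **2,000** |

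Rows two and three show that a single repeat by itself changes nothing. It matters only when part of the 2,000 mg portion is left. It then lowers the amount needed to pass: to 1,999 mg (1 mg repeated), 1,997 (3), 1,990 (10), 1,970 (30), 1,900 (100), 1,700 (300) or 1,000 mg (1,000 mg repeated). With one repeat of 1,000 mg, the conflict with the ED occurs only at exactly half the portion. If 1,000 mg and 300 mg are each repeated once, it covers x from 2,000 − 1,300 = 700 to 1,000 mg.

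**Weight of one child.** At the planned 220 and 110, 1/220 = 0.45 points and 1/110 = 0.91 points. The documents give no expected pass rate, so the placebo counts below are assumptions. The lower Newcombe bound is d − √[(p₁ − l₁)² + (u₂ − p₂)²], where d = p₁ − p₂, l₁ is the lower Wilson limit for active and u₂ the upper Wilson limit for placebo.

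| Placebo passes of 110 (assumed) | Smallest active count of 220 with bound > 0% | Bound there | Bound with one fewer |
|---|---|---|---|
| 0 | 9 | 0.21% | −0.18% |
| 1 | 13 | 0.27% | −0.13% |
| 2 | 16 | 0.12% | −0.28% |
| 3 | 19 | 0.07% | −0.34% |
| 5 | 25 | 0.14% | −0.27% |

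One child decides step 14 only when the result already lies on such a boundary.

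**The case against.** The strongest reply is that the sum is what part of the plan asks for. Protocol 6.1.1 and SAP 4.13 speak of the highest cumulative dose, 3,444 mg is that dose, and the rule parallels the 1,444 mg rule at step 9. This has weight: the sum follows naturally from that wording. But step 9 is named for a cumulative dose throughout, whereas step 14 is named for the highest dose in Protocol 3.2.1.2, SAP 3.2, the heading of SAP 4.8.3.7 and Table 2, and is equated with passing a challenge whose last step is 2,000 mg. The two names need reconciling, and the conflict with the ED rule remains under either.

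Second, the cases are narrow. Protocol 6.1.1.4 requires the challenge to continue to 2,000 mg unless objective reactions stop it, so a symptom-free stop part-way is a departure from procedure. That stands, although SAP 4.8.2 plans for it.

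Third, the earlier-step case depends on how intakes are recorded. The SAP's partial-dose rule covers only the last dose, 4.8.3.7 sums doses given, and neither the eCRF nor the challenge manual is available here. That also stands: the 3,429 mg example holds only if the shortfall is recorded.

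Fourth, simply requiring all 2,000 mg to be eaten would still disagree with SAP 4.8.2 when a few milligrams are left. This is correct, and the fix below allows for it.

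**Conclusion.** The point holds as a minor inconsistency of definition. Among children without stopping symptoms, the 3,444 mg rule can disagree with the ED rule in both directions, and it never requires the dose for which the endpoint is named. Each affected child moves a rate by 0.45 points (active) or 0.91 points (placebo). This assumes the planned numbers and that partial intakes are recorded as amounts eaten.

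A reader might infer more than the documents support:

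- That one repeated dose misclassifies a child. Alone it never does.
- That such cases are common. The documents give no frequency of repeats, partial doses or symptom-free stops.
- That a child who reacted could be scored as passing. The second condition excludes any child with a recorded ED.
- That other results are at risk. Step 14 is last, so no later test depends on it. The primary endpoint uses the ED, not the sum, and an ED of 1,000 or 2,000 mg meets the responder threshold in either screening subgroup.

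**What to change.** In SAP 4.8.3.7, replace the 3,444 mg sum with the event that SAP 4.8.2 already uses: the child took the 2,000 mg dose and had no objective symptom that ended the challenge. Count a partly eaten 2,000 mg portion by the partial-dose rule in 4.8.2, so that pass status and ED agree. In the table above, the two children scored as passing with an ED of 1,000 mg would become non-passes, and the two with an ED of 2,000 mg would become passes. One consequence should be stated openly: a child who eats more than 1,000 mg of the last portion would then pass. If the sponsor wants a stricter rule, the SAP should say so and note that the ED will differ.

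Use one name for the endpoint across Protocol 3.2.1.2 and 6.1.1 and SAP 3.2, 4.8.3.7, 4.13 and Table 2.

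The cost is one definition and a few aligned phrases. Protocol 6.1.1.3 and 6.2.1.3.6 already have doses given and symptoms entered in the e-CRF. Whether the amount eaten of a partial portion is also recorded should be confirmed. The change should be made before unblinding.
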